3.2 RATIONALE FOR STUDY DESIGN

This study is designed to evaluate the long-term safety and tolerability of ralinepag in subjects with PAH.

Inclusion of a placebo arm in Study APD811-003 and the requirement to maintain the blind in that study necessitates the re-titration of all subjects entering Study APD811-007. Thus, the dose titration scheme from Study APD811-003 will be employed in this study for subjects who were previously treated with placebo in Study APD811-003.

Optimal dosing of IP receptor agonists in PAH subjects requires dose titration on an individualized basis; furthermore, tolerability may improve with continued exposure.¹⁵ It is anticipated that the starting dose of 10 mcg BID will be tolerated by most, if not all, subjects. Data from the previous Phase 1 dose titration study suggests that there are individual differences in tolerability of ralinepag in healthy volunteers, consistent with findings from other studies of prostacyclin receptor agonists in PAH subjects.

Table 1 Schedule of Procedures and Visits: Study APD811-003 Subjects Treated with Ralinepag Entering Study APD811-007

Evaluation ^a	Baseline ^b (APD811-003 Week 25 Visit)	Treatment Period		End of Study (EOS)	28-Day Follow-Up ^c
		Q3 Months	1 or 2 Years		
		±5 days	±3 months	±3 days	±3 days
Informed consent	X				
Medical history	X				
Physical exam	X			X	
ECG (12-lead) ^d	X	X		X	
Clinical laboratory tests ^e	X	X		X	
Pregnancy test ^f	X	X		X	
Vital signs ^g	X	X		X	
Study drug administration	X ^h	X			
6MWT	X	X		X	
BNP/NT-proBNP ^k	X	X			
Assessment of clinical worsening	X	X		X	X
WHO/NYHA FC assessment ⁱ	X	X		X	X
RHC ^l			X		
Dose escalation/de-escalation assessment		X ^j			
Adverse event monitoring	X	X		X	X
Concomitant medication monitoring	X	X		X	X

Abbreviations: 6MWT, 6-Minute Walk Test; BNP, brain natriuretic peptide; ECG, electrocardiogram; FC, Functional Class; hCG, human chorionic gonadotropin; NT-proBNP, N-terminal pro-brain natriuretic peptide; NYHA, New York Heart Association; Q3, every 3; QTcB, QT interval corrected for Bazett’s formula; QTcF, QT interval corrected for Fridericia’s formula; RHC, right heart catheterization; RR, respiration rate; WHO, World Health Organization

^a Reference to pre-dose and post-dose activities in this schedule apply to the morning dose of study drug. Study drug should be taken with food.

^b The Week 25 (Day 175) Visit from Study APD811-003 will serve as the Baseline/Day 1 Visit for Study APD811-007.

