4.3 EXCLUSION CRITERIA

Subjects who meet any of the following criteria will be excluded from the study:

- Subjects who enrolled in Study APD811-003 and were withdrawn from study drug treatment due to any AE or SAE, or subjects who did not complete Study APD811-003, with the exception made as above for placebo-treated subjects who experienced a clinical worsening event.
- Female subjects who wish to become pregnant
- Systolic BP <90 mmHg at Baseline
- Other severe acute or chronic medical or laboratory abnormality that may increase the risk associated with study participation or investigational product administration or may interfere with the interpretation of study results and, in the judgment of the Investigator, would make the subject inappropriate for entry into this study.

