Prolonged dosing may result in tolerance to some adverse effects, so that consideration should be made to attempt dose escalation if some time (eg, >7 days) has elapsed since the prior dose escalation attempt and the 9-week Dose Titration Period is not yet complete.

In order to simplify dose titration, the 10 mcg strength capsule will be used during the initial portion of the dose titration.

If a subject reaches the highest dose tolerated (stable dose) and no further dose escalations are planned, the Dose Titration Period will be considered completed.

Table 3 Possible Dosing Regimen during 9-Week Dose Titration Period

Dose (mcg)		Supplied by		Total daily dose (mcg)
10	QD	1 × 10 mcg	QD	10
10	BID	1 × 10 mcg	BID	20
20	BID	2 × 10 mcg	BID	40
30	BID	3 × 10 mcg	BID	60
40	BID	4 × 10 mcg	BID	80
60	BID	3 × 20 mcg	BID	120
80	BID	4 × 20 mcg	BID	160
100	BID	5 × 20 mcg	BID	200
200	BID	2 × 100 mcg	BID	400
300	BID	3 × 100 mcg	BID	600

Abbreviations: BID, twice daily; QD, once daily

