9 STUDY POPULATION

9.1 SUBJECT ACCOUNTABILITY

A listing of subject disposition and ralinepag exposure will include the subject number, treatment group in the parent study, first and last ralinepag dose date/time in the APD811-007 study, date completed/discontinued the study, study drug exposure (weeks), reason for discontinuation, and any other details regarding reason for discontinuation. The summary of subject accountability will include the number (percent) of subjects who completed the study without early termination, the number of subjects who completed ralinepag treatment by each visit achieved, number of subjects who discontinued ralinepag treatment, and the reason for discontinuation. This summary will be provided by treatment group in the parent study and overall.

Ralinepag exposure and the total patient-years of ralinepag exposure will be summarized by the treatment group in the parent study and overall. Duration of treatment will be further characterized by weeks on the immediate-release and extended-release formulations.

In addition, for subjects who were in the ralinepag group of the parent study, exposure to ralinepag in the parent study will be combined into the APD811-007 study. The overall exposure to ralinepag across both the parent study and the APD811-007 study will be summarized.

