11 SAFETY ANALYSES

11.1 ADVERSE EVENTS

AEs are captured from the time the Informed Consent Form is signed. AEs that are ongoing at the parent study Termination Visit are recorded as continuing AEs in the APD811-007 study. All AEs with an onset date on or after the first dose of ralinepag in the APD811-007 study or AEs ongoing from the parent study will be included in data listings and summaries.

The AEs will be coded using the Medical Dictionary for Regulatory Activities, and all summaries will utilize the Preferred Term (PT) and/or System Organ Class (SOC). All AEs and serious adverse events (SAEs) will be organized by treatment group in the parent study and listed by subject number, including onset date (day) and time, stop date (day) and time, verbatim term, corresponding PT and SOC, seriousness, severity, relationship to study drug, action taken with study drug, and outcome.

The overall summary of AEs includes the number of subjects with any AE, the number of subjects with any study drug-related AEs, the number of subjects with AEs leading to study drug withdrawal, the number of subjects with any SAEs, the number of subjects with any severe AEs, and the number of subjects with any study drug-related severe AEs.

The summaries of AEs by SOC and PT will be provided by treatment group in the parent study and overall. The summaries of AEs, SAEs, severe AEs, AEs related to ralinepag, SAEs related to ralinepag, and AEs leading to permanent discontinuation of ralinepag will include the number (percent) of subjects and number of events for each reported PT.

The summary of AEs adjusted for length of ralinepag exposure will include the number (percent) of subjects and number of events for each reported PT, as well as the number of events per patient-years of exposure.

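### Table 14.3.1.9 gives one AE rate per patient-year for each parent arm and overall, so it cannot show how AE rates change with time on ralinepag; the overall rate also mixes new starters with subjects who completed about 25 weeks on drug, and AEs carried over from 003 are in the numerator

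*SAP*

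**What the plan says.** Long-term safety and tolerability is the primary objective (Protocol 2.1).

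**The rate.** The exposure-adjusted AE summary in SAP 11.1 (Table 14.3.1.9) gives, for each preferred term, subjects and events "as well as the number of events per patient-years of exposure". SAP 8 presents summary tables by parent treatment group and overall.

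**The numerator.** SAP 11.1 counts two kinds of event. The first kind is new-onset: "All AEs with an onset date on or after the first dose of ralinepag in the APD811-007 study". The second kind is carried over from 003 and is counted in both parent arms: "or AEs ongoing from the parent study will be included in data listings and summaries".

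**The denominator.** SAP 11.1 does not say which exposure is used. SAP 9.1 defines exposure within 007 and also a combined figure: "The overall exposure to ralinepag across both the parent study and the APD811-007 study will be summarized" (Table 14.1.3).

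**Who enters, and when.** For ex-ralinepag subjects, Table 1 of the protocol states: "The Week 25 (Day 175) Visit from Study APD811-003 will serve as the Baseline/Day 1 Visit for Study APD811-007". Protocol 4.3 excludes "Subjects who enrolled in Study APD811-003 and were withdrawn from study drug treatment due to any AE or SAE" and those who did not complete 003, with an exception only for placebo subjects who worsened. Protocol 5.6.1.2 and 5.7 have ex-ralinepag subjects continue on their 003 dose. Ex-placebo subjects titrate for up to 9 weeks inside 007 (Protocol 5.6.1.1).

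**Expected time course.** Protocol 3.2 says "tolerability may improve with continued exposure". Protocol 5.6.1.1 says "Prolonged dosing may result in tolerance to some adverse effects".

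**Timing of AEs.** Protocol 8.2.1 and 9.2.1.2 plan to tabulate AE onset in relation to dosing. No table in SAP 13.1 does so, and SAP 12 does not list this as a change.

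**The concern.** One events-per-patient-year figure describes AE burden well only if the rate is roughly constant on drug and the people averaged are at comparable stages of treatment. Neither can be taken for granted here.

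For ex-ralinepag subjects, 003 acts as a run-in. Those who left because of an AE are not in 007, and any AE that began and resolved during 003 is not counted. For ex-placebo subjects the starting and titration phase lies inside 007. The overall column averages the two groups, and each column averages the whole of follow-up. The table therefore cannot answer two questions that a long-term tolerability objective raises: do AEs fade with time on drug, and do any appear late?

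The numerator adds a second mismatch. An AE carried over from 003 began before the 007 exposure that would be its denominator, and in the ex-placebo arm it began on placebo.

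**Working it through.** The documents give no AE rate to reproduce, so the size has to be explored under stated assumptions.

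**Inputs from the documents**
- Prior time on drug of ex-ralinepag subjects at 007 entry: Day 175, so L = 175/365.25 = 0.479 year.
- Planned size of 007: approximately 60 (Protocol Synopsis). 003 had 61 subjects (Protocol 1.1.3); its allocation ratio is not stated.

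**Assumptions (not in the documents)**
- f, the ex-ralinepag share: 0.50 to 0.67.
- T, years of follow-up in 007: 1 to 4, the same in both arms.
- New-onset AE rate: k × r during the first L years on drug and r = 1 per year afterwards, with k from 1 to 5.
- No new titration phase for ex-ralinepag subjects at 007 entry, following Protocol 5.6.1.2 and 5.7.

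**Early drug time outside a 007-only rate.** With 30 to 40 ex-ralinepag subjects out of 60: 30 × 0.479 = 14.4 to 40 × 0.479 = 19.2 patient-years.

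**Formulas for the overall new-onset rate**
- 007 only: [f·T + (1−f)(kL + T − L)] / T
- From first ralinepag dose: [f(kL + T) + (1−f)(kL + T − L)] / [f(T + L) + (1−f)T]

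**Worked case: f = 2/3, T = 2, k = 3**
- Ex-ralinepag column in 007: 2/2 = 1.00.
- Ex-placebo column: (3 × 0.479 + 2 − 0.479)/2 = 2.958/2 = 1.48.
- Overall, 007 only: (2/3 × 2 + 1/3 × 2.958)/2 = 1.16.
- Overall, from first dose: (2/3 × 3.437 + 1/3 × 2.958) / (2/3 × 2.479 + 1/3 × 2) = 3.278/2.319 = 1.41.
- Ratio: 1.16/1.41 = 0.82, or 18% lower.

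**Break-even for carried-over AEs.** If each ex-ralinepag subject brings c ongoing AEs into the numerator, the overall 007 rate rises by f·c/T. The shortfall vanishes at c = (from-first-dose rate − 007 rate) × T/f. In the worked case this is (1.413 − 1.160) × 2/(2/3) = 0.76.

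**Over the full assumed range**

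| k (early/later risk) | 007 overall ÷ from-first-dose | Shortfall | Carried-over AEs per ex-ralinepag subject that cancel it |
|---|---|---|---|
| 1 | 1.00 | none | 0 |
| 2 | 0.85 to 0.95 | 5% to 15% | 0.3 to 0.4 |
| 3 | 0.76 to 0.91 | 9% to 24% | 0.6 to 0.9 |
| 5 | 0.67 to 0.85 | 15% to 33% | 1.2 to 1.7 |

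The shortfall shrinks as follow-up lengthens. The last column is for r = 1 per year and scales with r. Any carried-over AEs in the ex-placebo arm would lower the break-even.

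**If the denominator were combined exposure.** Dividing 007 events by 003 plus 007 exposure multiplies the ex-ralinepag rate by T/(T + L): 0.68 at T = 1, 0.81 at T = 2 and 0.89 at T = 4.

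**The case against.** The case for the plan has real substance.

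- **The parent-arm columns already separate the cohorts.** This stands. The ex-placebo column starts at first-ever ralinepag, and setting it beside the ex-ralinepag column gives a crude contrast of earlier and later treatment. The mixing problem is confined to the overall column. But each column is still one average over all follow-up, and the ex-placebo arm may include subjects who worsened on placebo, so the contrast is not a clean one of time on drug.
- **Listing 16.2.7 carries onset day.** It does, but SAP 8 counts study day from the first 007 dose. For ex-ralinepag subjects that is about 175 days short of time on drug, and a listing is not a rate.
- **The objective concerns subjects who completed 003, and the first 25 weeks were studied there under placebo control.** This stands against requiring 003 subjects who never entered 007, because they lie outside the SAP's Safety Population. It does not explain the absence of any display by time on drug.
- **The simple rate model ignores later titration.** This is correct. Protocol 5.6.2.1 has all subjects switch to the XR formulation during the study, with titration as needed, and 5.6.1.2 allows later dose increases. AEs may rise again then, in both arms.

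A reader might go further and infer that the 007 rate certainly understates ralinepag's AE burden, and that the true gap must exceed any calculated one because subjects who left 003 for AEs are missing. The documents do not support that. The tolerance statements are hedged ("tolerability may improve with continued exposure"; the other covers only some effects), no early or late rate is given, and carried-over AEs push the planned rate up.

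**Conclusion.** The point holds as one about what the planned rate can show. Table 14.3.1.9 averages over time in every column, and its overall column mixes new starters with subjects selected for completing 003 on drug. No table in SAP 13.1 shows AE rates by time on drug, although the protocol planned to tabulate onset relative to dosing.

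For new-onset AEs the likely direction is a 007 overall rate lower than the rate from first dose: 5% to 33% lower for an early-to-later risk ratio of 2 to 5, and no lower if risk is constant. These figures rest on an assumed ex-ralinepag share of 50% to 67%, 1 to 4 years of follow-up and a two-level rate. Once carried-over AEs are counted, the net direction cannot be fixed: about 0.3 to 1.7 per ex-ralinepag subject, at a later rate of 1 per year, would cancel the shortfall.

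A separate inconsistency bears on the calculation. Protocol 3.2 says that all subjects entering 007 need re-titration, whereas 5.6.1.2 and 5.7 have ex-ralinepag subjects continue on their 003 dose. These passages must be reconciled, because they decide whether that cohort has a titration phase inside 007.

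**What to change.** 1. **Match numerator and denominator.** State in SAP 11.1 that the rates in Table 14.3.1.9 are new-onset 007 events divided by 007 exposure. Show AEs carried over from 003 separately, outside the rate.
2. **Add AE rates by interval since first-ever ralinepag dose.** Time zero is 003 Day 1 for the parent-ralinepag arm and 007 Day 1 for the parent-placebo arm. Intervals could be 0–6, >6–12, >12–24 and >24 months, with events and patient-years matched within each interval, by parent group. Limit the display to all AEs, SAEs and the most common preferred terms so that cells do not become too sparse, and make time around the XR switch identifiable. For ex-ralinepag subjects in 007, 003 events and exposure can fill the first interval. That interval remains conditional on completing 003, so 003 ralinepag subjects who did not roll over can be added as an optional sensitivity display.
3. **Label the overall column** as mixing new starters with subjects who completed 003 on drug.
4. **Reconcile** Protocol 3.2 with 5.6.1.2 and 5.7 on titration at entry.

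The cost is SAP wording, one revised table and one extra table. Parent-study exposure for 007 subjects is already planned for Table 14.1.3; their 003 AE records would have to be added, and data on subjects who did not roll over would be needed only for the optional display. The downside is small numbers in the late intervals, with about 60 subjects in all.

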11.2 DEATHS

All deaths will be listed (including those occurring within 30 days of the last ralinepag dose) by subject number and will include the first ralinepag dose date in Study APD811-007, last ralinepag dose date in Study APD811-007, date of death, and cause of death. The summary of deaths will be presented by the parent study and overall and will include the number (percent) of

subjects who died (including those within 30 days of study participation) and their causes of death.

11.3 CLINICAL LABORATORY TESTS

The laboratory data will be listed by subject number and treatment group in the parent study, including all hematology and clinical chemistry parameters by visit. The listings will include the collection date/times (day), laboratory test, and results. The normal laboratory reference ranges will be included in the listings. A designation for low (L) or high (H) will be included for those laboratory values that are outside the relevant normal range. The listing of urinalysis and coagulation will also be presented by subject number and treatment group in the parent study and will include each scheduled and unscheduled urinalysis assessment. The laboratory sample collection date/time (day), laboratory test, normal range, designation for high or low, and analysis visit will be provided for each assessment, as well as the result of the test.

For hematology, clinical chemistry, and coagulation parameters, the original values and their changes from baseline (defined as the last measurement prior to the first dose of ralinepag in the APD811-007 study) will be summarized for each analysis visit by the treatment group in the parent study and overall. Shift tables for hematology and clinical chemistry will also be provided. For urinalysis results, the number (percent) of subjects within each category will be summarized for all analysis visits by treatment group in the parent study and overall.

Pregnancy test results for female subjects will be organized by treatment group in the parent study and listed by subject number and did the subject become pregnant during the study (yes/no).

11.4 VITAL SIGNS

The vital sign data will be listed by subject number and treatment group in the parent study for each visit by the assessment date/time (day), heart rate, systolic blood pressure, diastolic blood pressure, and respiratory rate. The original measures and their changes from baseline (defined as the last measurement prior to the first ralinepag dose in the APD811-007 study), and descriptive statistics will be summarized for all analysis visits by the treatment group in the parent study and overall.

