1.1.3 Summary of Clinical Data

The starting dose of 100 mcg for the first-in-human Study APD811-001 was determined in accordance with Food and Drug Administration (FDA) Guidance for Industry, *Estimating the Maximum Safe Starting Dose in Clinical Trials for Therapeutics in Adult Healthy Volunteers* (2005), and was based on the monkey NOAEL of 100 mcg/kg/day, using a safety factor of 20, and assuming a 60-kg human subject.

In Study APD811-001, up to 9 single ascending dose cohorts of 8 subjects each (6 active, 2 placebo) were planned. The administration of single doses of 30, 50, and 100 mcg were generally tolerated in healthy male and female subjects. The administration of a single dose of 200 mcg ralinepag was not well tolerated by subjects and resulted in discontinuation of further dose escalation in the study due to nausea and vomiting of severe intensity. The maximum tolerated dose in this clinical study was therefore 100 mcg. The adverse events (AEs) most commonly experienced included headache, vomiting, nausea, and jaw pain.

No consistent effects were seen on blood pressure (BP), but pulse rate appeared to increase more in ralinepag subjects than placebo subjects (delta ~10 bpm) at the 3 highest doses. Consequently, uncorrected QT interval decreased, but rate corrected QT interval for Fridericia's formula (QTcF) was increased from baseline at time of maximum plasma concentration (t_{max}) in nondose responsive fashion, by means and medians ranging from 3 to 9 msec at the 2 highest doses. An effect on QT interval is not supported by preclinical findings (human ether-à-go-go-related gene [hERG] concentration that inhibits 50% [IC₅₀] >20 μM, and no effect on QTc in a primate cardiovascular study at 3 to 4 times the C_{max} achieved in the Phase 1 study). No dose response on QT interval was seen, and the significance of the findings in this limited study is unclear.

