^c This visit may be conducted by telephone or in person based upon the Investigator’s discretion.

^d Safety ECGs should be completed pre-dose. After the last subject enrolled in Study APD811-007 completes approximately 6 months of treatment and a cumulative all-subject data analysis is performed, as outlined in Section 9 (Planned Statistical Methods), ECGs will subsequently be conducted locally at the discretion of the

- Investigator (as clinically indicated) during the Q3 monthly visits. The ECG will be performed at the End of Study Visit. Locally collected ECG values for RR, PR, QRS, QT, QTc, QTcB, and QTcF will be collected in the Sponsor's clinical database.
- ^e Clinical laboratory tests will include hematology, serum chemistry, coagulation, and urinalysis. Clinical laboratory tests will be completed pre-dose. After the last subject enrolled in Study APD811-007 completes approximately 6 months of treatment and a cumulative all-subject data analysis is performed, as outlined in Section 9, clinical laboratory tests will subsequently be conducted locally at the discretion of the Investigator (as clinically indicated) during the Q3 monthly visits. A complete clinical laboratory test will be conducted locally at the End of Study Visit. Locally collected laboratory values that are abnormal and clinically significant will be collected in the Sponsor's clinical database along with the reference ranges.
 - ^f Serum hCG pregnancy tests will be completed pre-dose at each visit during the Treatment Period. After the last subject enrolled in Study APD811-007 completes approximately 6 months of treatment and a cumulative all-subject data analysis is performed, as outlined in Section 9, pregnancy testing (either serum or urine) will subsequently be conducted locally during each Q3 monthly and the End of Study Visit. Locally collected positive values for hCG will be collected in the Sponsor's clinical database along with the reference range.
 - ^g Vital sign measurements (blood pressure, heart rate, respirations, and body temperature taken in supine position after 5 minutes of rest) will be taken pre-dose.
 - ^h Subjects treated with ralinepag in Study APD811-003 study will continue on current dose.
 - ⁱ WHO/NYHA Functional Class will be assessed pre-dose at all visits.
 - ^j An assessment for further dose escalation or de-escalation will be conducted during the Q3 months.

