5.7 METHOD OF ASSIGNING SUBJECTS TO TREATMENT GROUPS

All subjects will receive ralinepag in this study. Subjects randomized to placebo during Study APD811-003 will begin a Dose Titration Period until a stable dose is reached. Subjects randomized to ralinepag during Study APD811-003 will start on the final dose achieved during that study. Subjects who remain on ralinepag at study termination and meet all eligibility criteria are eligible to roll into the open-label extension study (ROR-PH-303).

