8.4 ASSESSMENT WINDOWS

For efficacy and safety assessments, baseline is defined as the last measurement prior to the first dose of ralinepag in the APD811-007 study.

Summary analyses will usually be based on the scheduled (nominal) visits with no visit windows applied. If appropriate, hemodynamic parameters will only be summarized by the Baseline and post-Baseline Visits of APD811-007.

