11.5 SAFETY ECG

Individual ECG values will be listed by treatment group in the parent study and visit. They will be summarized using descriptive statistics. Intervals to be provided for each ECG are: respiratory rate, PR, QRS, QT, QT interval corrected, QT interval corrected for Bazett's formula, and QT interval corrected for Fridericia's formula. Post-baseline ECGs will be compared with the baseline ECG. Summary statistics will also be provided for change from baseline in ECG values. The baseline value is defined as the last measurement prior to the first ralinepag dose in APD811-007.

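### Safety change-from-baseline and shift tables use an on-ralinepag baseline for ex-ralinepag subjects and a ralinepag-free one for ex-placebo subjects, so the overall change column averages two different quantities

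*SAP*

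**What the plan says.** SAP 8.4 sets one rule for all assessments: "For efficacy and safety assessments, baseline is defined as the last measurement prior to the first dose of ralinepag in the APD811-007 study". SAP 11.3 repeats it for laboratory tests ("defined as the last measurement prior to the first dose of ralinepag in the APD811-007 study"), SAP 11.4 for vital signs ("defined as the last measurement prior to the first ralinepag dose in the APD811-007 study") and SAP 11.5 for ECGs ("The baseline value is defined as the last measurement prior to the first ralinepag dose in APD811-007"). SAP 8 presents every summary table by parent-study arm and overall.

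Protocol 7.2.1.1 makes the parent-study Week 25 measurements the extension baseline. For dosing at entry, a footnote to Table 1 states "Subjects treated with ralinepag in Study APD811-003 study will continue on current dose", and protocol 5.7 states "Subjects randomized to ralinepag during Study APD811-003 will start on the final dose achieved during that study". Ex-placebo subjects start ralinepag in the extension.

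Protocol 9.2.1.4 to 9.2.1.6 call for comparison with baseline in vital signs, laboratory values and ECGs without defining baseline there. The parent-study Day 1 definition stands in the efficacy section, 9.2.2. SAP 12 declares a change of baseline for efficacy values only. Neither document plans a safety analysis against parent-study Day 1.

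**The concern.** One column heading carries two meanings. For an ex-placebo subject, change from baseline compares values on ralinepag with values before any ralinepag. For an ex-ralinepag subject it compares later values on ralinepag with Week 25 values on ralinepag. A shift in pulse, blood pressure, QTc or a laboratory value that arose in the parent study and persisted has an expected change of about zero in the second group.

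Protocol 9.2.1 makes safety the primary analysis and names laboratory values, vital signs and ECG findings within it. Ex-ralinepag subjects also have the longer exposure, which is what a long-term safety study is meant to describe. The protocol gives reasons to look at these measures: 1.1.3 reports that "pulse rate appeared to increase more in ralinepag subjects than placebo subjects" at the three highest single doses, reflex tachycardia at higher doses in the multiple-dose study, and a Grade 3 transaminase increase in the XR study.

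The SAP is also uneven. Section 9.1 adds parent-study ralinepag exposure to extension exposure, so exposure can be counted from the first-ever dose while measured change is not.

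**Working it through.** The documents state no figure on this point to reproduce. The check compares the baseline rule with the dosing rule, then works out the arithmetic of the overall column.

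**1. State at baseline, by parent arm**

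| Parent arm | Extension baseline | Ralinepag at that time |
|---|---|---|
| Ralinepag | Week 25 (protocol 7.2.1.1; SAP 8.4) | Yes; parent-study dose carried on (protocol 3.1, Table 1 footnote, 5.6.1.2, 5.7) |
| Placebo | Week 25, or the end-of-study assessment after clinical worsening | No |

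**2. Does pre-dose timing make the Week 25 value drug-free?** Protocol 1.1.3 gives a half-life of 20.5 to 26.4 h. Assuming simple exponential decline, the fraction of drug level left after t hours is 2^(−t / half-life).

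- 12 h: 2^(−12/20.5) = 0.67 and 2^(−12/26.4) = 0.73
- 24 h: 2^(−24/20.5) = 0.44 and 2^(−24/26.4) = 0.53

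So it does not. With twice-daily dosing, about two thirds or more of the level remains at the next pre-dose time.

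**3. Expected mean change.** Let D be the drug effect at an extension visit, p the part of it already present at Week 25, and f the ex-ralinepag share of subjects with a value at that visit.

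- Ex-ralinepag: (1 − p) × D
- Ex-placebo: D
- Overall: f × (1 − p) × D + (1 − f) × D = (1 − f × p) × D

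With the effect fully present at Week 25 (p = 1), this becomes 0, D and (1 − f) × D.

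**4. Illustration.** D = 10 bpm is the approximate pulse difference from placebo in protocol 1.1.3, for single doses in healthy volunteers; its persistence is assumed. The documents do not give the parent-study split, so f is an assumed range.

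| f | Ex-ralinepag | Ex-placebo | Overall, p = 1 |
|---|---|---|---|
| 0.33 | 0 | 10 | 6.7 |
| 0.50 | 0 | 10 | 5.0 |
| 0.67 | 0 | 10 | 3.3 |
| 0.75 | 0 | 10 | 2.5 |

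If only half the effect was present at Week 25 (p = 0.5), the overall figure is (1 − 0.50 × 0.5) × 10 = 7.5 bpm at f = 0.50 and (1 − 0.67 × 0.5) × 10 = 6.65 bpm at f = 0.67.

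**5. Same illustration on a pre-ralinepag baseline.** Both arms show D, so overall = f × 10 + (1 − f) × 10 = 10 bpm for any f.

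**6. Shift tables.** A laboratory value that went from normal to high in the parent study and stayed high is tabulated as high at baseline and high later. The abnormality is visible, but it is not counted as a shift on ralinepag.

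**The case against.** A reader might infer that drug effects are removed from the primary safety evaluation as a whole. The documents do not support that. The primary outcome measures listed in the protocol synopsis are treatment-emergent AEs and SAEs, which use no measured baseline. Observed laboratory, vital-sign and ECG values are summarized alongside the changes, and laboratory listings flag low and high results. The ex-placebo column keeps its ralinepag-free baseline and is shown separately. Changes after Week 25, including any that follow dose increases or the XR switch, remain visible in both arms.

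A reader might also infer that the SAP departs from a protocol safety baseline. It does not: it follows protocol 7.2.1.1, and parent-study Day 1 is specified for efficacy only. Change since extension entry is a coherent long-term question, and the first 25 weeks were covered by a randomized placebo-controlled comparison, which isolates drug effect better than any uncontrolled change.

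The remedy has limits too. Over an open-ended extension, change from parent-study Day 1 also contains disease course and permitted changes in background therapy. After the six-month cumulative analysis, laboratory tests and ECGs become local and discretionary, and only abnormal, clinically significant local laboratory values enter the database. A new baseline does not cure that selection.

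All of this stands, and it narrows the point without removing it. Summaries of observed values give no within-subject change from pre-drug status and no corrected shift counts. Separate columns do not make the overall change column interpretable.

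**Conclusion.** The point holds for three displays: the ex-ralinepag change columns for laboratory values, vital signs and ECGs; the ex-ralinepag laboratory shift tables; and the overall columns built on them. The first two measure change since Week 25 on ralinepag. The overall change shrinks any effect fully present at Week 25 to (1 − f) of its size, so an assumed 10 bpm becomes 5.0 to 3.3 bpm for an assumed f of 0.50 to 0.67.

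That figure illustrates the mechanism and does not estimate anything for this trial. It comes from volunteers, protocol 1.1.1 allows that patients may respond differently, and both persistence and f are assumed. For QTc, protocol 1.1.3 regards prolongation as unlikely in the dose range studied.

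Calling the Week 25 dose stable would also go further than the text, which speaks of a current or final dose. Protocol 3.2 says that keeping the parent-study blind "necessitates the re-titration of all subjects entering Study APD811-007", which conflicts with 3.1, the Table 1 footnote, 5.6.1.2 and 5.7. These passages must be reconciled. On either reading, the Week 25 values of ex-ralinepag subjects were taken on ralinepag.

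**What to change.** In SAP 8.4 and 11.3 to 11.5:

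- Keep the extension-entry baseline, and label it in each table as on-treatment for ex-ralinepag subjects.
- Add a supplementary change and shift analysis against the last value before the first-ever ralinepag dose: parent-study Day 1 pre-dose for ex-ralinepag subjects, and the last value before the first extension dose for ex-placebo subjects. Apply it to Tables 14.3.4.1 to 14.3.4.4 and 14.3.4.6 to 14.3.4.8.
- Report overall change only on this common pre-ralinepag baseline, with a note that the interval is longer and uncontrolled for ex-ralinepag subjects.

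Separately, reconcile protocol 3.2 with 3.1, the Table 1 footnote, 5.6.1.2 and 5.7 on dosing at entry.

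The cost is low but not zero. No visit or sample is added, and the SAP already brings in parent-study exposure, height and weight. Parent-study Day 1 laboratory, vital-sign and ECG data must be mapped into seven tables.
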